18. RESEARCH RELATED HARM/INJURY

- *Describe the availability of medical or psychological resources that subjects might need as a result of anticipated problems that may be known to be associated with the research.*
- *If the research is greater than minimal risk, explain any medical treatments that are available if research-related injury occurs, who will provide it, what will be provided, and who will pay for it.*

Research-related injuries are not expected for this no greater than minimal risk project.

19. POTENTIAL BENEFIT TO SUBJECTS

- *Explain what benefits might be derived from participation in the study, noting in particular the benefit over standard treatment (e.g. a once-a-day administration instead of four times a day, an oral formulation over an IV administration).*

- *Also state if there are no known benefits to subjects, but detail the value of knowledge to be gained*

Although not a primary endpoint, participants randomized to the intervention may receive an indirect benefit, i.e., they may gain a better understanding of how melatonin personally affects them or could possibly see a positive effect on their sleep disturbance symptoms. This may result in their being more satisfied with their sleep quality wellness regimen and in achieving reduced sleep disturbance symptoms. Through pooling N-of-1 trial data, a greater understanding of the effectiveness of melatonin will arise. Through comparing N-of-1 interventions with usual care (during the baseline run-in and placebo periods), participation by all subjects will also contribute to the understanding of the effects of engaging patients with sleep quality issues in N-of-1 trials, and this knowledge may contribute to the incorporation of N-of-1 trials into the clinical practice of sleep quality management. Additionally, the information collected from participant involvement will inform the development of future Personalized Trials to help other research participants and eventually patients discover which wellness options are best for them as an individual.

20. PROVISIONS TO PROTECT PRIVACY INTERESTS OF SUBJECTS

- *Describe the methods used to identify potential research subjects, obtain consent and gather information about subjects to ensure that their privacy is not invaded.*
- *In addition consider privacy protections that may be needed due to communications with subjects (such as phone messages or mail).*

Names and email addresses from potential study participants will not be collected until they have read through web information explaining the research study and protocol and indicated their interest in the study. This information will be stored in a Northwell-approved database drive to store PHI, and it will only be accessible to research staff listed on the approved IRB protocol. Names or other identifying information will not be shared with those outside the research team, except as indicated in the “Data Management and Confidentiality” section above for the purposes of sending research communications. Phone numbers and email will only be used for study-related communications, and employees will be contacted outside the study for future research opportunities only as indicated in the consent document.

21. COSTS TO SUBJECTS

- *Describe any foreseeable costs that subjects may incur through participation in the research*
- *Indicate whether research procedures will be billed to insurance or paid for by the research study.*

This research study is funded by the National Institutes for Health (NIH). All study related equipment, devices, supplements, and placebos will be provided to participants at no cost. Participant insurance will not be billed.

This study uses text messaging to deliver notifications, reminders, and study questionnaires. Standard message and data rates from the participant's wireless carrier may apply to the study participant. Study participants will not be compensated for any costs related to data usage or sending or receiving text messages by the study or by members of the study team.

22. PAYMENT TO SUBJECTS

- *Describe the amount of payment to subjects, in what form payment will be received and the timing of the payments.*

Study participants will receive ClinCard valued at \$100 after successful completion of the study. As a thank you, participants will also be able to keep the Fitbit device.

23. CONSENT PROCESS

If obtaining consent for this study, describe:

- *Who will be obtaining consent*
- *Where consent will be obtained*
- *Any waiting period available between informing the prospective participant and obtaining consent*
- *Steps that will be taken to assure the participants' understanding*
- *Any tools that will be utilized during the consent process*
- *Information about how the consent will be documented in writing. If using a standard consent form, indicate such.*
- *Procedures for maintaining informed consent.*

Consent and written authorization will be obtained electronically via the N1Thrive by 4Peacocks platform, with a copy of the electronically signed form sent to the participants with their study instructions and devices. Before being sent a copy of the consent form, potential participants will be sent through a series of web pages that summarize the study, as well as collect pre-screening information with written authorization.

If a prospective participant is deemed ineligible, or if the potential participant is eligible but needs to be waitlisted due to demand, the consenting coordinator

will notify the potential participant via text within 2 business days of the initial completion date of the pre-screen.

If the potential participant is deemed eligible, potential participants will opt in or out of having a 30-minute virtual call to go over study details with a consenting coordinator, and have the opportunity to have any of their questions answered. After the phone call takes place, the consenting coordinator will send the potential participant a text with a link to read and electronically sign the consent form. If the participant opts out of having the call, they will be sent a link to read and electronically sign the consent form. Included at the link sent to participants who opted in and out of the call will be a short, animated video that explains key aspects of the protocol and consent process. Included in these materials will be contact information to reach a consenting coordinator to answer any additional questions they have before signing the consent form. In order for the consent form to be signed and submitted successfully, potential participants will need to correctly answer 4 questions about the protocol to demonstrate their understanding. PDF versions of signed consent forms will be maintained electronically on a HIPAA-compliant, Northwell Health-approved share drive, accessible only to members of the research team listed on the IRB protocol. A copy of the consent form and signed signature page will be sent to the potential participant along with their baseline study material.

In the state of NY, any participants under the age of 18 are considered children. If your study involves children, additional information should be provided to describe:

- *How parental permission will be obtained*
- *From how many parents will parental permission be obtained*
- *Whether permission will be obtained from individuals other than parents, and if so, who will be allowed to provide permission. The process used to determine these individual's authority to consent for the child should be provided*
- *Whether or not assent will be obtained from the child*
- *How will assent be documented*
- *Whether child subjects may be expected to attain legal age to consent to the procedures for research prior to the completion of their participation in the research. If so, describe the process that will be used to obtain their legal consent to continue participation in the study. Indicate what will occur if consent is not obtained from the now-adult subjects.*

N/A

If the study involves cognitively impaired adults, additional information should be provided to describe:

- *The process to determine whether an individual is capable of consent*
- *Indicate who will make this assessment*

- *The plan should indicate that documentation of the determination and assessment will be placed in the medical record, when applicable, in addition to the research record.*
- *If permission of a legally authorized representative will be obtained,*
 - *list the individuals from who permission will be obtained in order of priority*
 - *Describe the process for assent of subjects; indicate whether assent will be required of all, some or none of the subjects. If some, which subjects will be required to assent and which will not.*
 - *If assent will not be obtained from some or all subjects, provide an explanation as to why not*
 - *Describe whether assent will be documented and the process to document assent*
 - *Indicate if the subject could regain capacity and at what point you would obtain their consent for continued participation in the study*

N/A

If the study will enroll non-English speaking subjects:

- *Indicate what language(s) other than English are understood by prospective subjects or representatives*
- *Indicate whether or not consent forms will be translated into a language other than English*
- *Describe the process to ensure that the oral and written information provided to those subjects will be in that language*
- *If non-English speaking subjects will be excluded, provide a justification for doing so*

Our goal for this research is to test virtual research delivery capabilities for the digital health technology used for this specific use case. While there may be some personal benefit derived, the study is not designed to seek out or document any specific benefit, and our primary outcome measure is devoid of such calculation. We are focused on soliciting feedback from participants on the ease of platform use, if the research delivery was satisfactory, if the participant report was deemed useful, etc. In the future, it will be especially important to obtain this feedback from individuals who are non-English speaking, and the intention once we document minimum use requirements, acceptability, and proof of greater effectiveness over traditional research methods through our project's forthcoming RCT, is to seek funding so that we can work with N-1 Thrive to build virtual delivery capabilities that are fit-for-purpose in research involving individuals who are non-native English speakers. Having a platform capable of accurately displaying research requirements and study related material is especially important for speakers whose language involves characters that may not be easily displayed electronically or may introduce formatting errors. We aim to be transparent that further research is needed to assess feasibility in the

same delivery with non-English speaking individuals. Presently we hope to collect enough information to justify that this methodology offers greater benefit than standard RCT delivery to make the case that more significant financial investment should be made to have the platform scaled to larger clinical trials designed to assess safety and/or efficacy of the given interventions (e.g. melatonin). Injustice has no place in research with human subjects and undermines public trust in science, thus we are committed to enrolling a racially and ethnically diverse population in this protocol and for all research conducted by the Institute for Health System Science. Towards that commitment, we anticipate that many participants interested in this current research project will represent racial and ethnic minority groups, and we intend to advertise the research without restriction. Race and ethnicity (not just English proficiency) are strongly correlated with access to care, environmental exposures, income, employment, and other social determinants of health, which, by definition, affect health outcomes. We will collect information on all of these factors to help inform virtual research delivery and do not believe that focusing on native English speaking participants in this pilot study - those that may be from ethnically and racially diverse populations - will confirm pre-existing bias or will later negatively impact equitable access, participant comprehensibility or research design applicability to the diverse populations that may be solicited for participation in future clinical trials run under an N-of-1 design. We would be happy to further discuss considerations for equality in research and ways we as researchers and ethics professionals can address bias and structural injustices.

24. WAIVER OR ALTERATION OF THE CONSENT PROCESS N/A

Complete this section if you are seeking an alteration or complete waiver of the consent process.

- *Describe the possible risks of harm to the subjects involved in this study and explain why the study involves no more than minimal risk to the subject:*
- *Explain why the waiver/ alteration will not adversely affect the rights and welfare of subjects*
- *Explain why it is impracticable to conduct this research if informed consent is required*
- *Explain why it is not possible to conduct this research without using the information or biospecimens in an identifiable form*
- *If appropriate, explain how the subjects will be provided with additional pertinent information after participation. If not appropriate to do so, explain why.*

Since the consent process will be remote and self-directed, it is not practicable or feasible for the investigator to sign the consent form in N1Thrive or RedCap. As such, we request a waiver of the investigator's signature for this research which is no greater than minimal risk. Individuals are encouraged to reach out to the

study team via email and/or a direct phone line if they have any questions and prior to signing the consent form.

Complete this section if you are obtaining informed consent but you are requesting a waiver of the documentation of consent (i.e., verbal consent will be obtained). To proceed with a waiver based on these criteria, each subject must be asked whether they wish to have documentation linking them to this study. Only complete subsection 1 OR subsection 2.

SUBSECTION 1

- *Explain how the only record linking the subject to the research would be the consent document.*
- *Explain how the principal risk of this study would be the potential harm resulting from a breach in the confidentiality*
- *Indicate whether or not subjects will be provided with a written statement regarding the research.*

SUBSECTION 2

- *Describe the possible risks of harm to the subjects involved in this study and explain why the study involves no more than minimal risk.*
- *Confirm that the research only involves procedure for which consent is not normally required outside the research context.*
- *Indicate whether or not subjects will be provided with a written statement regarding the research.*

25. WAIVER OF HIPAA AUTHORIZATION

N/A

Complete this section if you seek to obtain a full waiver of HIPAA authorization to use and/or disclose protected health information.

- *Describe the risks to privacy involved in this study and explain why the study involves no more than minimal risk to privacy:*
- *Describe your plan to protect identifiers from improper use or disclosure and to destroy them at the earliest time.*
- *Indicate why it is not possible to seek subjects' authorization for use or disclosure of PHI.*
- *Indicate why it is not possible to conduct this research without use or disclosure of the PHI.*
- *Indicate if PHI will be disclosed outside NSLIJ Health System, and if so, to whom.*

Note: PHI disclosed outside NSLIJ Health System, without HIPAA authorization needs to be tracked. Please see guidance at www.nslij.com/irb for information about tracking disclosures.

--

Complete this section if you seek to obtain a partial waiver of the patient's authorization for screening/recruitment purposes (i.e., the researcher does not have access to patient records as s/he is not part of the covered entity)

Note: Information collected through a partial waiver for recruitment cannot be shared or disclosed to any other person or entity.

- *Describe how data will be collected and used:*
- *Indicate why you need the PHI (e.g. PHI is required to determine eligibility, identifiers are necessary to contact the individual to discuss participation, other)*
- *Indicate why the research cannot practicably be conducted without the partial waiver (e.g. no access to medical records or contact information of the targeted population, no treating clinician to assist in recruitment of the study population, other)*

--

26. VULNERABLE POPULATIONS:

Indicate whether you will include any of these vulnerable populations. If indicated, submit the appropriate appendix to the IRB for review:

Children or viable neonate
 Cognitively impaired
 Pregnant Women, Fetuses or neonates of uncertain viability or nonviable
 Prisoners
 NSLIJ Employees, residents, fellows, etc
 poor/uninsured
 Students
 Minorities
 Elderly
 Healthy Controls

If any of these populations are included in the study, describe additional safeguards that will be used to protect their rights and welfare.

This study is not targeting employees or students. However, all employees of the health system, as well as graduates and students of Hofstra University are eligible to participate in the study. Northwell Health has the most diverse employee workforce in the state of New York and it services a vast number of individuals from racial and ethnic minority groups. Hofstra University also has a significant number of students

who identify as racial/ethnic minorities. As such, we expect a diverse subject population.

Individuals with a supervisory relationship over an employee will not enroll any individual who reports to them in this study. Employee participation or non-participation in this study will have no bearing on an individual's position at Northwell Health.

Similarly, professors or supervisory staff will not enroll individuals who report to or work or study under them. Student-participation or non-participation will have no bearing on an individual's position at Hofstra University or Northwell Health. |

We do not intend to prevent study personnel or other employees of the Institute of Health System Science who express an interest in the research from participating. However, no supervisory personnel will be able to enroll participants who report to them in this research. We are not intentionally targeting minorities, but expect minorities to be part of those eligible for participation.

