10. ENDPOINTS

- *Describe the primary and secondary study endpoints*
- *Describe any primary or secondary safety endpoints*

This study is a feasibility pilot whose primary objective is to assess the acceptability, scalability of implementation, and participant satisfaction with a personalized trial methodology to resolve a chronic complaint. Thus, the primary endpoint is the system usability scale (SUS) $\geq 85^{22}$.

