Ten days into the baseline period, a Consenting Coordinator will review individual adherence to Fitbit wear and to survey responses. Adherence to Fitbit wear will be defined as recorded activity of greater than 12 hours a day, and recorded sleeping activity greater than 180 minutes in total. Survey adherence will be defined as submission of a given survey. Baseline participants who do not achieve at least 80% adherence of Fitbit wear and survey submission during the first 10 days of the baseline period will be given until day 14 of the trial to obtain 80% adherence. Those who still do not meet 80% adherence by day 14 will be withdrawn from the study. Those participants who do maintain at least 80% adherence during the baseline period will be randomized to one of two intervention sequences in the pilot study. Participants who are randomized to receive intervention sequences will receive confirmation including their protocol timeline. Participants will also receive a second mailed kit including medication adherence devices containing pills of a 3mg dose melatonin, pills of a 0.5mg dose melatonin, and pills of a placebo. Participants will not know when they are taking 3 mg melatonin, 0.5 mg melatonin or placebo (single blinded). Enrollment will continue until up to 60 participants have been randomized overall, with 30 participants randomized to receive ABCCBA and 30 participants randomized to receive CBAABC.

Each intervention sequence is made up of 6 2-week periods assigning either 3mg dose melatonin, 0.5mg dose melatonin, or placebo. Participants will not be aware of which pill they are taking in assigned intervention weeks. Instead, they will receive a text notification each night asking them to take one pill out of a designated container (A, B, or C) 1 hour before bed. Melatonin or placebo will be tracked remotely through electronic adherence pill bottles that record each event of a pill being removed via a cellular connection to a de-identified dashboard. Throughout each intervention sequence, participants will be asked to refrain from taking additional melatonin on their own.

Melatonin and placebo supplements will be stored at the study team office from delivery until time of dispensation to participants upon their randomization into the intervention period. The supplements will be handled only by study personnel and stored according to labeling. Records of the batch numbers of supplements provided to each participant will be maintained.

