12. STATISTICAL ANALYSIS

- *Describe how your data will be used to test the hypotheses.*
- *State clearly what variables will be tested and what statistical tests will be used.*
- *Include sample size calculations.*
- *If this is a pilot study, state which variables will be examined for hypothesis generation in later studies.*

The sample size of 60 participants was chosen to have a sufficient number of patients to obtain a preliminary assessment of the feasibility of personalized trials of sleep quality with melatonin compared to a placebo. The numbers of sleep quality reports, questionnaires, and intervention repetitions per trial were based on expert recommendations by a statistician and estimations about maximal duration of the trial to maintain patient engagement. With n=60 randomized participants, expecting a trial completion rate of 70%, we anticipate SUS data are available in

about $n = 42$ participants, thus giving a standard error no greater than 8% in estimating the rate of SUS $\geq 85^{22}$. The standard error will be the largest when the trial completion rate is at 50%. Data will be reported transparently so that individual level heterogeneity can be assessed²³.

Participants will be randomized into one of two different intervention orders, ABCCBA or CBAABC, where A=3mg dose melatonin, B=.5mg dose melatonin, and C=placebo. Although participants will be aware of their randomization order (i.e. 'A' weeks, 'B' weeks, and 'C' weeks), they will be blinded to each letter's corresponding supplement or placebo until their participant summary report. Two intervention orders were chosen to test out the feasibility of carrying out a virtual, N-of-1 study. ABCCBA was chosen as an order to test participant acceptability with back-to-back single-blinded placebo intervention (i.e., no intervention) extending through 4 weeks. CBAABC was chosen as a companion intervention order to ABCCBA to test participant acceptability with starting a Personalized Trial with a single-blinded placebo after a baseline run-in (i.e., no intervention for the first 4 weeks). Intervention order was not included as a factor in the statistical analysis because this is an acceptability and feasibility study.

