The randomization schedule will be set up by a member of the Institute of Health System Science data team and provided to the data analyst assigned to Personalized Trials to Improve Sleep Quality. Randomization will occur with a fixed seed value for the purposes of repeatability and auditability, and the list of 60 participants will be split into two groups of 30 using a random shuffle function that takes that seed as input. The order in which an individual becomes eligible for one of these 60 randomizations will determine the placement given (i.e. the first person eligible will be randomized to the intervention order given to participant 1, and continue sequentially). Eligibility is obtained by a participant maintaining at least 80% adherence of survey response, Fitbit wear ≥ 12 hours a day 80% of days, and 80% sleep data ≥ 180 minutes available through the baseline run-in period. The data analyst will alert the research coordinator of the assigned randomization once a participant becomes eligible during the baseline run-in period. As this pilot is not blinded to study coordinators, this concealed allocation involving the data analyst alerting the study coordinator of intervention assignment will be used to prevent bias by blinding the sequence up until time of randomization.

The primary outcome measure will be a mean usability score, obtained using the System Usability Scale (SUS), a validated 10-item questionnaire originally developed by John Brooke in 1986 that asks users to score each item on a Likert scale from Strongly Disagree (rating of 1) to Strongly Agree (rating of 5). The SUS will be presented to the participant as addressing the ease of use, complexity, consistency of the Personalized Trials system as a whole, from recruitment to receipt of the report. Individual results are calculated to arrive at a composite measure out of 100. Participant SUS scores will be averaged together. Higher scored values correlate to a more usable system, and therefore a better outcome.

Other secondary outcome measures which assess the feasibility of the Personalized Trials framework include:

- Mean participant satisfaction with Personalized Trials components supplemental to the SUS,
- Qualitative satisfaction data collected during the virtual participant follow-up interview,
- Mean participant survey adherence rate, defined as completion of each assigned survey

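### Study personnel may take part, so staff who know the letter code and have a stake in the system can contribute to the primary SUS

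*Combined protocol and SAP*

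**What the plan says.** Section 26 says of staff: "We do not intend to prevent study personnel or other employees of the Institute of Health System Science" from participating if they are interested. For this group the section offers a rule about reporting lines, that "no supervisory personnel will be able to enroll participants who report to them in this research", and an assurance that participation has no bearing on a person's job. The inclusion and exclusion lists in Section 7 do not mention study staff.

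Section 10 makes the SUS, with a threshold of 85, the primary endpoint. Section 12 says that it covers the "consistency of the Personalized Trials system as a whole, from recruitment to receipt of the report", and that "Participant SUS scores will be averaged together". No section flags, removes or separately analyses staff scores.

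On blinding, Section 11 says that participants will not know which product they are taking. Each night a text tells them which of containers A, B and C to use. Section 12 says that participants know their letter order but "they will be blinded to each letter's corresponding supplement or placebo until their participant summary report". The same section sets out one key for both sequences: A = 3 mg melatonin, B = 0.5 mg, C = placebo. It adds: "As this pilot is not blinded to study coordinators". Section 5 requires staff to stay informed about the protocol.

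**The concern.** Two separate problems follow from letting study personnel take part.

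The first is a conflict of interest on the primary endpoint. The SUS is meant to show whether participants find the system usable, and staff would be rating a process that they run. The rule on reporting lines deals with pressure to enrol. It does nothing about how a staff member scores the system.

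The second is that the blind is not available to these people. Someone who works from a protocol that contains the key cannot take part as a blinded participant, so the statements in Sections 11 and 12 cannot hold for them. This bears on the self-reported sleep, symptom and side-effect outcomes in Section 12, and on goal 4 in Section 4, which concerns attitudes to a single-blinded protocol with a placebo.

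A lesser matter is that one letter code appears to serve all participants. If someone receives a report while others are still dosing, that report could reveal the code to anyone who hears of it.

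**Working it through.** **The plan's own figures.** Section 12 gives 60 randomized and 70% completion, so 60 × 0.70 = 42 SUS respondents. The largest binomial standard error (SE), at a 50% rate of SUS ≥ 85, is √(0.5 × 0.5 / 42) = 7.72%. This agrees with the stated bound of 8%.

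**Shift in the rate of SUS ≥ 85.** Let k of the 42 respondents be staff who all score 85 or more, and let p be the rate among the other 42 − k. Both are assumptions, because the plan gives neither.

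Observed rate − p = [(42 − k)p + k]/42 − p = (k/42)(1 − p).

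| k | p = 0.3 | p = 0.5 | p = 0.7 |
|---|---|---|---|
| 1 | 1.7 points | 1.2 | 0.7 |
| 2 | 3.3 | 2.4 | 1.4 |
| 3 | 5.0 | 3.6 | 2.1 |
| 5 | 8.3 | 6.0 | 3.6 |
| SE at n = 42 | 7.07 | 7.72 | 7.07 |

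For k = 2 the shift is 3.33/7.07 = 0.47 SE at p = 0.3, 2.38/7.72 = 0.31 SE at p = 0.5, and 1.43/7.07 = 0.20 SE at p = 0.7. One or two staff therefore move the rate by less than half an SE over this range. A shift of one full SE needs k = 42 × SE/(1 − p), which is 4.2, 6.5 and 9.9 staff raters respectively.

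**Shift in the mean SUS.** Section 12 also defines the primary outcome as a mean. If staff score d points above the others (an assumption), the mean rises by k × d/42. With d = 5, 10 and 20, this is 0.4, 0.7 and 1.4 points for k = 3, and 0.6, 1.2 and 2.4 points for k = 5. If d is negative, the mean falls by the same amount.

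**Precision if staff are left out of the 42.** The maximum SE is √(0.25/41) = 7.81% with one removed, √(0.25/40) = 7.91% with two, and √(0.25/39) = 8.01% with three.

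**Common code and timing.** Section 9 allows at most 20 people per start date, so 60 participants need at least 60/20 = 3 dates. It promises the report within 3 months of study completion, without saying whether that means the individual's or the whole study's.

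- If it means the whole study's, no report goes out while anyone is dosing.
- If it means the individual's, someone who starts g weeks after an earlier participant, with no pauses, is still dosing when that person's report arrives only if g exceeds the delay between completion and report. The plan gives neither g nor the actual delay, so overlap is possible but not shown.

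**The case against.** The strongest reply is that the effect may be trivial. Section 26 says that employees are not targeted. A staff member would still have to meet the insomnia screen, pass the exclusions and reach 80% baseline adherence. One or two raters would hardly matter, and nothing shows that staff would score high. All of this stands as a limit on size. It does not remove the problem, because the plan sets no cap on staff participants and the stated SE does not capture a systematic difference in their ratings.

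A reader might infer more than the documents support, in four ways:

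- That three staff could move the rate by 3/42 = 7.1 points, about the stated 8% SE. That shift needs a rate of zero among all other respondents, whereas the 8% bound applies near 50%. The two figures do not belong together.
- That staff ratings necessarily bias the SUS upward. The plan gives neither the number of such raters nor the direction of any difference.
- That one disclosure would unblind all 60 participants. It reaches only those who hear it while still dosing, and Section 9 leaves open whether reports go out in that window. Recruitment under Section 6 extends well beyond one employer and one university, so contact between participants is uncertain.
- That a leaked code would distort the primary endpoint. Section 11 sends the satisfaction survey after the report, and Section 12 has the SUS cover receipt of the report. Completers therefore give their ratings after their own report has unblinded them.

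It is also fair to say that the team did not build everything being rated. Section 14 describes a separate company that supplies the platform. The conflict rests on the team running the system.

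**Conclusion.** The point holds. The plan lets study personnel take part, counts their scores in a primary outcome that rates the system they run, and describes as blinded some people who can know the key. The conflict and the lack of blinding follow directly from the text. The size is conditional: with 3 staff among 42 respondents, all scoring 85 or more, the rate shifts by 2.1 to 5.0 points for p from 0.7 to 0.3. This should be corrected because the remedy is cheap, not because the primary result is shown to be wrong.

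The common code is a secondary matter. That all bottles share one code is read from Sections 11 and 12 together, since no section describes the physical labels. Any leak would bear on the self-reported secondary outcomes and goal 4, and only if reports and dosing overlap.

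**What to change.** **Main change.** Add to the Section 7 exclusions all personnel listed on the IRB submission and Institute staff with access to the code. The loss of eligible people is negligible: Section 5 cites over 70,000 employees and over 11,000 students, before social media. Because the rule acts at eligibility, the planned 60 randomized and the expected 42 respondents are unchanged.

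**If such staff are enrolled.** State in Section 12 that they are left out of the primary SUS and of the blinded comparisons, and report the SUS with and without them. The cost is a maximum SE of 7.8% to 8.0% if one to three are removed from 42.

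**Optional.** Generate a participant-specific letter-to-product code with the randomization list, so that a report reveals only its recipient's code. This takes more than relabelling: bottle labels, nightly texts, the mapping of adherence data and the reports must all follow each person's code.
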